Patients were randomized using even numbered blocks in a 1:1 fashion. Treatment allocation was sealed in opaque, sequentially numbered envelopes. After screening was performed and eligibility determined, a member of the treatment team opened the sealed envelope and informed the bedside nurse of the treatment allocation. A sign was then placed on the door of the patient with treatment allocation to inform all staff of the patient's involvement in the study and the treatment allocation.

Study Intervention:

Patients in a UAB ICU who were intubated and in whom the treating physician planned on initiating prone positioning for COVID-induced ARDS were screened for inclusion and exclusion criteria. Inclusion and exclusion criteria were documented on the screening form, and baseline ABG and ventilator settings were documented. Following enrollment, an opaque envelope was opened revealing treatment allocation. The bedside nurse was provided with a form stating the treatment allocation.

If patients are randomized to the traditional proning arm, the patient will be placed in the prone position for 16 hours. Following the 16-hour prone session, the patient will be returned to the supine position. After 4 to 6 hours in the supine position, an ABG is to be drawn. If the P:F ratio is < 150 while on 10 cmH₂O of PEEP and 60% FiO₂, the patient will be returned to the prone position. If the patient is not immediately eligible for reproning at this time but subsequently has a P:F ratio of < 150 on requisite ventilator settings, they will be repositioned to the prone position. This process will be continued as long as the patient was eligible. The patient will remain in the same treatment allocation arm.

If randomized to the prolonged proning arm, the patient will be placed in the prone position for 24 hours. Following the 24-hour prone session, the patient will be returned to the supine position. After 4 to 6 hours in the supine position, an ABG will be drawn. If the P:F ratio is < 150 while on 10 cmH₂O of PEEP and 60% FiO₂, the patient will be returned to the prone position. If the patient is not immediately eligible for reproning at this time but subsequently has a P:F ratio of < 150 on requisite ventilator settings, they will be repositioned to the prone position. This process will be continued as long as the patient was eligible. The patient will remain in the same treatment allocation arm.

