All other care will be directed by the treating team and/or unit/hospital protocols.

Data Collection:

Data collection will be performed through a combination of data collection forms completed by the treatment team and EMR abstraction.

Sample Size Calculation:

This study was designed as a pilot study to evaluate the safety and feasibility. We anticipated an 8h change in duration prone and a standard deviation of 10h along resulting in an initial sample size of 52 patients.

DSMB & Interim Analysis:

Given the pace of enrollment and relatively small sample size, no interim analysis will be performed. This study will be stopped early for poor recruitment if enrollment drops below 8 patients enrolled on a rolling 4-week period.

Statistical Analysis:

Stata 16.1 (StataCorp, College Station, TX) will be used for all statistical analysis. Continuous variables will be presented as means with standard deviation or median with interquartile range. Comparisons will be made with the student's t-test or Mann-Whitney U test, as appropriate. Categorical variables will be reported as frequencies and proportions. Categorical variables will be compared using the Chi² test. A p-value of 0.05 will be considered significant.

Handling of Missing Data:

We have planned for no missing data in our power calculation.

Specific Aim 1:

Determine if the protocolized use of prolonged prone positioning results in an increased duration prone in the first 96 hours after proning

Hypothesis:

Patients randomized to receive prolonged prone positioning will spend more hours prone.

Specific Aim 2:

Compare the effect of traditional prone-positioning to prolonged prone-positioning on physiologic data, specifically improvements in P:F ratio and pulmonary mechanics.

Hypothesis: Patients who undergo prolonged prone positioning will have improved physiologic characteristics on day 4 when compared to those in the standard prone duration arm, as measured by P:F ratio and driving pressure.

Research Plan Overview: We propose a pragmatic, open-label, randomized trial of 52 patients in a 1:1 ratio to traditional proning strategy vs. prolonged proning.

Plan for Consent: We will perform this study under waiver of informed consent based on HHS Code of Federal Regulation (45 CFR 46).

IRB Category: Expedited review – Approved

Expected Duration of Study: We expect this study to last approximately 5-6 months at a rate of 8-10 patients enrolled per month.

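### Does leaving Aim 1 to either a t-test or a Mann-Whitney test, with no rule for choosing, need to be changed?

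*Combined protocol and SAP*

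**What the plan says.** The Statistical Analysis section has one rule for comparing continuous variables: "t-test or Mann-Whitney U test, as appropriate". It gives no criterion for what is appropriate, and it leaves the summary open in the same way, between mean with SD and median with IQR.

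Specific Aim 1 asks whether prolonged proning gives "increased duration prone in the first 96 hours after proning". Its hypothesis is "Patients randomized to receive prolonged prone positioning will spend more hours prone", and it names neither a mean, a median nor a rank measure.

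The Sample Size Calculation section reads: "We anticipated an 8h change in duration prone and a standard deviation of 10h along resulting in an initial sample size of 52 patients". It states no power, sidedness or test. The Research Plan Overview adds the design: "We propose a pragmatic, open-label, randomized trial of 52 patients in a 1:1 ratio".

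The Study Intervention section sets sessions of 16 or 24 hours. It then says for the traditional arm, and in near-identical words for the prolonged arm: "After 4 to 6 hours in the supine position, an ABG is to be drawn". Sessions repeat while the oxygenation criterion is met.

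**The concern.** The sample size appears to target a difference in mean hours, while the analysis text does not commit to one. For many outcomes this would hardly matter, because the two tests usually agree. Here the schedule makes the outcome lumpy and capped. A patient with one session contributes 16h or 24h, so ranks can separate the arms cleanly on session length while variation in the number of sessions inflates the SD and hides the mean difference.

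Two things would be at stake. First, in an open-label trial, Aim 1 could be called positive or negative on one dataset, with nothing in the plan to say which result stands. Second, the meaning could shift. Re-proning depends on the P:F ratio, and Aim 2 expects that "Patients who undergo prolonged prone positioning will have improved physiologic characteristics on day 4". If the prolonged arm therefore needs fewer sessions, mean hours could be equal while Mann-Whitney still reports more hours prone.

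**Working it through.** **1. The plan's own figure.** Inputs from the Sample Size Calculation section: difference 8h, SD 10h, so d = 8/10 = 0.8. Assumed: two-sided 5%, 80% power. The noncentral t calculation needs 25.5 per arm, hence 26 per arm and 52 in total. Power at 26 per arm is 80.7%. By the same method, one-sided 80% gives 42 and two-sided 90% gives 68, so the two-sided 80% t-test is the natural reading. If Mann-Whitney were the planned test under normality, 25.5/(3/π) = 26.7, or 27 per arm and 54 in total. The two tests are two patients apart.

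**2. Possible outcome values.** With a 5h supine break, totals over 96h are 16, 32, 48, 64 or 76h (traditional) and 24, 48, 72 or 81h (prolonged).

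**3. A dataset on which the verdicts differ.** Assume re-proning probability 0.5 at each check in both arms (the documents give none). Expected counts are 13/6/3/2/2 patients with 1 to 5 traditional sessions and 13/7/3/3 with 1 to 4 prolonged sessions.

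- Means: 824/26 = 31.7h and 1107/26 = 42.6h, a gap of 10.9h.
- SDs: 20.0h and 21.7h, pooled 20.9h.
- t = 10.9/(20.9 × √(2/26)) = 1.88 on 50 df, p = 0.066; 95% CI -0.7 to 22.5h.
- Mann-Whitney: U = 13×13 + 7×20.5 + 3×24 + 3×26 = 462.5 out of 26×26 = 676, a probability of 0.68 that a prolonged-arm patient has more hours (ties counted half); p = 0.020.

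Both tests favour the prolonged arm. The SD is twice the planned 10h and the standardised gap is 10.9/20.9 = 0.52 rather than 0.8, so a borderline p-value is unsurprising.

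**4. How often verdicts differ.** Simulated trials of 26 per arm, supine break uniform on 4 to 6h, same constant re-proning probability in both arms:

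| Assumed probability | Pooled SD (h) | Power, t-test | Power, Mann-Whitney | Verdicts differ |
|---|---|---|---|---|
| 0.10 | 7 | 99% | 100% | 1% |
| 0.15 | 9 | 96% | >99% | 3% |
| 0.20 | 11 | 92% | >99% | 8% |
| 0.30 | 14 | 78% | 95% | 18% |
| 0.50 | 20 | 58% | 72% | 17% |
| 0.70 | 24 | 45% | 57% | 14% |
| 0.90 | 20 | 35% | 96% | 61% |

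Nearly all the differences are Mann-Whitney significant and the t-test not. In none of these patterns did a simulated trial have the tests significant in opposite directions. With an exponential eligible time instead, a mean of 12h gives SD 7.9h and 12%, and a mean of 18h gives SD 12.4h and about 36%. Of 13 expected-count datasets with the same pattern in both arms, 4 split and 9 agree.

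**5. Cost of free choice.** With identical arms, calling the result positive if either test has p<0.05 gives about 5.4 to 6.5% in the patterns first run. Rechecking with 20,000 trials per pattern gave about 5 to 6.6% in nearly all, 7.1% at probability 0.8 and 7.7% at 0.9. The ceiling for two 5% tests is 10%.

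**6. Equal means.** Re-proning probabilities (traditional against prolonged) chosen so that mean hours are equal:

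| Probabilities | Relative cut in re-proning | t-test rejects | Mann-Whitney rejects |
|---|---|---|---|
| 0.4 vs 0.09 | 1 - 0.09/0.4 = 78% | 6% | about 40% |
| 0.5 vs 0.23 | 1 - 0.23/0.5 = 54% | 5% | about 22% |
| 0.6 vs 0.37 | 1 - 0.37/0.6 = 38% | 5% | 11% |
| 0.7 vs 0.5 | 1 - 0.5/0.7 = 29% | 5% | 7% |

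**The case for a change.** The best case for a change is that Aim 1 drives the sample size, is judged at 0.05 without blinding, and feeds the argument for a larger trial. One sentence naming the test would remove the ambiguity at no cost in patients. The disagreement is also not confined to wild SDs: the exponential pattern with mean 18h reaches about 36% at an SD only a little above plan. And a Mann-Whitney result could be positive with no gain in mean hours, the quantity that seems to have set the sample size.

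The facts in that case stand. The inference weakens on three counts.

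- The large disagreement rates come mostly from SDs well above the planned 10h, and all rest on eligibility patterns the documents do not supply.
- The equal-mean cases that produce a sizeable gap need longer sessions to cut re-proning by half or more. The Expected Results section anticipates only a trend in mechanics. Even then Mann-Whitney is not in error: the distributions differ, and the hypothesis of more hours prone names no mean.
- The obvious remedy, fixing the t-test, is not clearly better. It matches the sample size and gives an answer in hours, but it usually loses power (78 against 95% at probability 0.3). In an even split of one and two sessions it gains power instead (99 against 90%). A statistician facing lumpy, truncated data could reasonably choose either.

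**Conclusion.** No change to the plan follows. The plan leaves a choice unwritten, and an analyst can fill it sensibly with either permitted test: both are valid against the null of no difference between arms, and they nearly always point the same way. What can differ is whether one effect clears 0.05. Under constant re-proning that happens in about 1 to 9% of trials near the planned SD, in about 14 to 60% at SDs of about 14 to 24h, and in about 36% in one exponential pattern near 12h. The price of using whichever test is significant is a false-positive rate of about 5 to 6.6% in nearly all patterns, and just under 8% at worst.

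The stakes are modest. The trial is a safety and feasibility pilot, Aim 1 is largely a check that 16h and 24h assignments separate the arms, and no decision is tied to its p-value. Naming one test with its matching summary would be tidy, but which one is a trade-off for the sponsor rather than a correction.

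This rests on assumed power (80%), two-sidedness, the reading of 8h and 10h as Aim 1 inputs, and assumed re-proning patterns that ignore death and extubation within 96 hours.

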**Prolonged Prone Positioning for COVID-19-induced Acute
Respiratory Distress Syndrome (ARDS): A Pilot Study**

NCT 04581811

Date of Protocol: 10/1/2020

Prolonged Prone Positioning for COVID-induced ARDS

Primary Investigator: [name]
Address: [name]
[name]
Mailbox: [name]

[name], K, [name], [name], [name], [name], [name]

Introduction:

The Novel Coronavirus has resulted in a pandemic of patients with respiratory failure, the most ill subset of which are experiencing Acute Respiratory Distress Syndrome (ARDS). Few therapies have demonstrated efficacy in treating this novel illness.[1-4] Prone ventilation is one of the few interventions known to decrease mortality in ARDS.[5] Prone positioning has become ubiquitous with the COVID-19 pandemic, expanding to even include non-intubated patients and now getting attention in the lay press.[6-10]

A major limitation to the most impactful implementation of prone positioning is that the ideal duration of prone ventilation is unknown. The landmark study on prone positioning demonstrating a mortality benefit used a 16 hour prone session followed by a supine period.[5] The rationale behind using a 16h strategy was not based on physiologic or outcomes data. There is retrospective, observational data suggesting that improvements in oxygenation may increase with duration of prone positioning extending beyond 16 hours to at least 24 hours. [11, 12] Further, decreasing the number of times position is changed decreases nursing burden and may decrease the rate of inadvertent line or tube displacement, the most feared complication of proning. Other potential risks associated with the act of changing position include transient changes in hemodynamics and oxygenation which would also be expected to occur less frequently with prolonged proning.

Early in the pandemic, we noticed that some patients experienced severe desaturations when returned to the supine position. This led to an alteration in clinical practice where patients were left in the prone position for longer than the standard 16 hours, some up to 72 hours. Given the recent emphasis on prone positioning, the variation in clinical practice and the protracted course of mechanical ventilation experienced by patients with COVID-ARDS, we felt there was equipoise to evaluate prolonged prone positioning in a prospective fashion.

This study was designed as a pilot safety and feasibility study.

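### A safety and feasibility pilot plans significance tests at p = 0.05 but no interval estimates, so it will not show how much harm 26 patients per arm leave unexcluded

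*Combined protocol and SAP*

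**What the plan says.** The Introduction gives the purpose: "This study was designed as a pilot safety and feasibility study". The Sample Size Calculation section repeats it: "This study was designed as a pilot study to evaluate the safety and feasibility".

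The Statistical Analysis section plans means with SDs or medians with interquartile ranges, and counts with proportions. For inference it gives three sentences: "Comparisons will be made with the student's t-test or Mann-Whitney U test, as appropriate"; "Categorical variables will be compared using the Chi² test"; and "A p-value of 0.05 will be considered significant". No confidence interval, safety margin or threshold for feasibility success appears anywhere in the document.

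The sample size rests on a process measure: "We anticipated an 8h change in duration prone and a standard deviation of 10h along resulting in an initial sample size of 52 patients". The Research Plan Overview confirms a "randomized trial of 52 patients in a 1:1 ratio to traditional proning strategy vs. prolonged proning", which is 26 per arm. Specific Aims 1 and 2 cover hours prone in the first 96 hours, and P:F ratio and driving pressure on day 4. No safety outcome is listed. The Introduction mentions line or tube displacement as a feared complication, but only as rationale.

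**The concern.** A pilot on safety and feasibility has to say what it learned about harm and how precisely. A test at 0.05 answers a narrower question: whether the observed difference would be surprising if the arms were equal. When the sample was sized for something else, the likely answer is 'not significant' whether or not the intervention does harm. With no events in either arm, the Chi² statistic cannot even be calculated.

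The section on DSMB and interim analysis rules out an interim look, and its only stopping rule concerns recruitment. The final analysis is therefore the only planned between-arm comparison of any adverse event. The Potential Significance section says that a successful result could justify a large multicentre trial. Whoever makes that decision needs to know what size of harm the pilot has and has not ruled out.

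**Working it through.** **Inputs.** From the documents: difference 8 h, SD 10 h, total 52, allocation 1:1 (so 26 per arm), significance level 0.05. Not stated: power and sidedness; two-sided testing is assumed below. No adverse-event rates are given, so every rate and count in steps 2 to 4 is an assumption, shown over a range.

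**Step 1. The plan's own figure.** Normal approximation, two-sided 5%, 80% power:

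n per arm = 2 × (1.960 + 0.842)² × (10/8)² = 2 × 7.85 × 1.5625 = 24.5, rounded up to 25, total 50.

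The t-distribution version needs 25.5, so 26 per arm and exactly 52. Power at 26 per arm is then 80.7%. The 80% two-sided basis is inferred: one-sided testing at 90% power gives 54 by the normal approximation, which is also close. On either basis, 52 reflects hours prone and not a harm.

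**Step 2. What Chi² can detect at 26 per arm.** Exact power of the uncorrected Pearson test is the sum, over all 27 × 27 possible pairs of counts, of the binomial probabilities of the pairs with p < 0.05. The last column is the normal-approximation size for 80% power:

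n = [1.960 × √(2p̄(1−p̄)) + 0.842 × √(p₁(1−p₁) + p₂(1−p₂))]² / (p₁−p₂)², where p̄ is the mean of p₁ and p₂.

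| Assumed rates | Exact power, 26 per arm | n per arm for 80% power |
|---|---|---|
| 5% v 10% | 8.6% | 435 |
| 5% v 15% | 22.4% | 141 |
| 10% v 20% | 18.1% | 199 |
| 20% v 40% | 36.8% | 82 |

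By the normal approximation, the smallest increase detectable with 80% power is about 31 points from 5%, 34 from 10%, 37 from 20% and 38 from 30%.

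**Step 3. No events.** For 0/26 in one arm, the exact two-sided 95% upper limit is 1 − 0.025^(1/26) = 13.2%. For 0 v 0, each Wilson upper limit is 1.96²/(26 + 1.96²) = 3.84/29.84 = 12.9%, so the Newcombe interval for the difference is −12.9 to +12.9 points.

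**Step 4. Some events, test not significant.** Newcombe 95% intervals, in percentage points:

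| Assumed events (of 26 each) | Chi² p | Difference | 95% interval |
|---|---|---|---|
| 3 v 3 | 1.00 | 0 | −19.0 to +19.0 |
| 3 v 0 | 0.074 | +11.5 | −3.4 to +29.0 |
| 4 v 1 | 0.158 | +11.5 | −6.1 to +30.0 |
| 8 v 3 | 0.090 | +19.2 | −3.3 to +39.9 |
| 13 v 7 | 0.087 | +23.1 | −3.2 to +45.4 |

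Every row would be reported as not significant. Only the interval shows how much harm remains possible.

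**Step 5. Hours prone.** At the planned SD, the 95% half-width for the mean difference is t(0.975, 50) × 10 × √(2/26) = 2.009 × 2.774 = 5.6 h. The test is informative for this outcome; the interval adds its precision.

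**The case against.** The best defence is that the plan contains no faulty decision rule. A reader might infer that a non-significant test will be reported as showing safety, that the larger trial depends on such a test, or that the test is the whole basis for a safety statement. The documents support none of these. The 0.05 sentence is a general significance level. Progression depends on a success that is left undefined, and the Expected Results section speaks of feasibility and a trend in pulmonary mechanics, not of a safety p-value. With no safety outcome named, no safety test is specified either. This stands.

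Descriptive summaries are also planned. With counts and arm sizes a reader can derive the intervals for proportions, and means with SDs give the interval for a mean difference. This largely stands: what is missing is mainly presentation, except where only medians and quartiles are shown. It does not replace a commitment, made before results are known, on how an uncertain safety result will be worded.

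The event rates are assumed. True, and at 20% v 40% power is 37%: low, but not negligible. Across the assumed pairs shown, power stays below 40%.

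Finally, the missing safety outcome may be the larger gap. That is fair, but whichever events are eventually reported, they will need intervals.

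**Conclusion.** The point holds as a cheap improvement, not as an error in the plan. Significance testing is the only inferential method planned for a pilot whose stated purpose is safety and feasibility, and at 26 per arm a non-significant Chi² result would tell little about safety. Under the assumed counts above, such a result is compatible with absolute increases in harm of roughly 13 to 45 points.

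The absence of interval estimates, the basis of the sample size and the arm sizes come directly from the documents. The power figures and intervals rest on assumed event rates and counts, two-sided testing, the uncorrected Pearson test and complete data on all 52 patients. On the last of these the plan says: "We have planned for no missing data in our power calculation". Losses would widen the intervals.

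**What to change.** Add to the Statistical Analysis section:

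- Each adverse-event proportion (for example line or tube displacement, named in the Introduction) and each feasibility proportion will be reported with an exact 95% confidence interval per arm and a Newcombe 95% confidence interval for the risk difference.
- Hours prone, P:F ratio and driving pressure will be reported as between-arm differences with 95% confidence intervals.
- A non-significant test will not be taken as evidence of safety.

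The cost is a few sentences. Sample size, data collection and the existing tests stay as they are. The one drawback for the sponsor is a less favourable safety statement, since even an event-free result would carry an upper limit of about 13 points.

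This does not complete the safety plan. The adverse events and feasibility measures to which the intervals apply still have to be defined.

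### Aim 2 does not fix the time origin, hour, window or body position of the day-4 P:F and driving-pressure readings, so prone and supine values can be mixed within and between arms.

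*Combined protocol and SAP*

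**What the plan says.** The Specific Aim 2 section compares the arms on physiology, "specifically improvements in P:F ratio and pulmonary mechanics". Its hypothesis is that the prolonged arm will show "improved physiologic characteristics on day 4 when compared to those in the standard prone duration arm", with P:F ratio and driving pressure as the measures. It gives no time origin, hour, window, rule for choosing among several readings, or body position. It also does not say whether an improvement means a change from baseline or a day-4 value.

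Three nearby passages come close, but none is tied to Aim 2:
- Specific Aim 1 counts "increased duration prone in the first 96 hours after proning", for hours prone only.
- Study Intervention calls for an ABG after 4 to 6 hours supine in both arms, in order to decide on re-proning (P:F below 150 on the stated PEEP and FiO₂). Beyond that, "All other care will be directed by the treating team and/or unit/hospital protocols".
- At enrolment "baseline ABG and ventilator settings were documented", but no analysis is said to use them.

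Data Collection names forms and EMR abstraction, without a schedule of readings. Statistical Analysis offers the "t-test or Mann-Whitney U test, as appropriate". The missing-data section is one sentence, "We have planned for no missing data in our power calculation", and gives no rule for patients who die or are extubated before day 4.

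**The concern.** Body position at the reading is not incidental here. The re-proning rule uses the P:F ratio, so position on day 4 depends on the outcome being analysed: the patients with the worst oxygenation are the ones still being cycled and most likely to be read prone. If prone readings run higher, the worst values are raised in both arms, more often in the arm with more sick patients, and a true difference shrinks.

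The two arms also run on different cycles, so a reading taken at one clock hour can find one arm prone and the other supine. That would bias the comparison even if the strategies were equivalent.

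The trial is open-label. With no reading named, someone who knows the allocation may have to choose among several ABGs. Potential Significance says that the data could help justify a multicentre trial, so the physiologic comparison should be interpretable.

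**Working it through.** **1. The plan's own figure.** Inputs from Sample Size Calculation: "We anticipated an 8h change in duration prone and a standard deviation of 10h", total 52, 1:1, significance level 0.05. Power and sidedness are not stated; 80% and two-sided are assumed. The effect is 8/10 = 0.8 SD. The t-test then needs 25.5 per arm, so 26 per arm = 52. The figure is reproduced, but it concerns hours prone. With 26 per arm and 80% power the detectable difference is 0.792 SD, used below as the reference effect for P:F.

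**2. Schedule.** Start the clock at first proning, with uninterrupted cycling. Supine periods in hours 72-96:

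| Supine time | 16 h arm | 24 h arm | Prone hours, each arm |
|---|---|---|---|
| 4 h | 76-80 | 80-84 | 20 |
| 5 h | 79-84 | 82-87 | 19 |
| 6 h | 82-88 | 84-90 | 18 |

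A patient still cycling is prone for 18/24 = 75% to 20/24 = 83% of that day in either arm, but not at the same hours. With 5 h supine, only the 16 h arm is supine at hours 79-82, and only the 24 h arm at hours 84-87.

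**3. Dilution in raw units.** Assumptions: true supine difference 0.792 SD; re-proning threshold at the pooled median, so 0.654 of one arm and 0.346 of the other lie below it (gap 0.308); reading at a random time in hours 72-96.

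Observed difference = 0.792 − gain × prone share × 0.308.
- Gain 0.25 SD: 0.734 (share 0.75) to 0.728 (share 0.83)
- Gain 0.5 SD: 0.677 to 0.664
- Gain 1 SD: 0.561 to 0.535

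These are about 0.73, 0.67 and 0.55 SD.

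**4. Dilution in the units the test uses.** Raising the low values also narrows the spread. By simulation under the same set-up, the SD falls from 1 to about 0.93, 0.87 and 0.80. Then 0.73/0.93 = 0.785, 0.67/0.87 = 0.77 and 0.55/0.80 = 0.69, against 0.792. Allowing for rounding and the range of prone shares, the loss is about 1-2%, 3-4% and 13-14%. Simulated t-test power (40,000 runs, 26 per arm) goes from 80% to about 79%, 78% and 69%.

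**5. No true effect.** If both arms have the same prone share, position adds no bias. If one hour finds them in different positions, bias = gain × fraction still cycling × difference in prone share. With half the patients cycling and all in step (difference 1, the extreme), this is 0.125, 0.25 or 0.5 SD for the three gains. The sign depends on the hour chosen. Varying supine times and delays would make it smaller.

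**6. Early loss.** Assume no true effect and that the patients lost are the worst on a latent score correlated 0.3 to 1 with the value. With 2 versus 4 deaths of 26, the arm with more deaths looks better by 0.04-0.12 SD; with 2 versus 5, by 0.05-0.18 SD. With equal losses arising in the same way, the bias is 0. The standard error is √(2/26) = 0.28 with all patients and √(1/24 + 1/22) = 0.30 with 2 and 4 lost.

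**7. Cost of ranking deaths worst.** Assume a true 0.79 SD effect, 4 deaths in each arm and latent correlation 0.5. Mann-Whitney power is about 50% with deaths ranked worst and about 73% among survivors.

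**8. Width of the window.** The longest gap between supine ABGs in a cycling patient is 24 + 6 = 30 h, which is the length of hours 72-102. Under illustrative delays, a window of hours 72-96 holds a supine ABG for all cycling patients in the 16 h arm but only 90-92% in the 24 h arm; hours 72-102 hold one for all in both. Without delays, the reading nearest hour 96 falls on average at (100 + 84 + 88)/3 ≈ 91 in the 16 h arm and (84 + 87 + 90)/3 = 87 in the 24 h arm.

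**The case against.** The best defence is that the plan nearly answers the point. Aim 1 sits directly above Aim 2 and uses a 96-hour clock, which is four days. The only ABG scheduled after baseline is supine in both arms. An analyst who used it would have position-matched readings, and the 75-83% prone share would be an upper scenario. This is fair as a guess at intent, but neither passage is linked to Aim 2, and an ABG does not supply driving pressure. It supports the fix more than it removes the gap.

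Three stronger readings are tempting, and the documents do not support them:
- **Position costs up to about 30% of the effect.** That is so only in raw units and for a gain of 1 SD. In the units of the test the loss is about 13-14% even then, and a few per cent or less for the smaller gains. The Introduction reports that some patients desaturated severely on being turned supine; this makes a gain plausible but gives no figure.
- **Unhandled deaths and extubations seriously bias Aim 2.** No rates are given. The illustrated bias is at most 0.18 SD beside a standard error of about 0.28-0.30, and the imbalances used arise easily by chance (Fisher p = 0.67 for 2 versus 4, 0.42 for 2 versus 5). The Introduction's long ventilator courses, and the exclusion of patients with DNR orders or severe haemodynamic instability, suggest modest loss by day 4.
- **The main analysis must therefore rank deaths worst.** This can cost over 20 points of power when deaths do not differ by arm, and it replaces a physiologic question with a composite.

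It is also true that Aim 2 is not the basis of the sample size and that only a trend is expected.

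**Conclusion.** The point holds as a gap in the definition of the reading, with minor to moderate weight. Following the plan as written can mix prone and supine values, in a way that depends on the outcome and, at a given hour, on the arm's cycle. The likely cost to the P:F test is small unless the prone gain approaches 1 SD. The possible bias from reading the arms in different positions has no predictable sign and could matter if one fixed hour were used.

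All the sizes rest on assumed prone gains, threshold, deaths and correlations, none of which the documents give. No position effect on driving pressure has been quantified. The absence of a rule for early loss is real, but it calls for clear reporting and not for a different main analysis.

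**What to change.** State in the plan:
1. Time runs from first proning, as in Aim 1.
2. In both arms the reading is the supine ABG closest to hour 96 within one common window, hours 72-102, with the ventilator values charted at that time for driving pressure.
3. P:F is compared with adjustment for the baseline ABG value already documented, for example by a linear model with arm and baseline P:F.
4. Deaths and extubations before hour 96, and available readings, are tabulated by arm. The comparison is described as one among patients with a reading.
5. A ranking with death worst and extubated-alive best may be added, as a sensitivity analysis only.

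The cost is some wording, plus abstracting position and time with each ABG from sources already planned. No treatment changes. Some patients who stayed supine may lack a reading in the window, because no further ABG is scheduled for them; driving pressure may not be charted at the chosen time; and readings will not fall at exactly the same hour in the two arms.
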